	
quartiles were calculated according to Brookmeyer and Crowley methods (55,56). Safety data were analysed throughout the entire study.
 
In the first step to develop a prediction model for PFS, univariate Cox regression analysis including all clinical variables collected in the study was performed in order to identify which should be considered for the model selection thereafter in the second step. All factors with a ≤ 0.15 p value (Appendix 15.2, item 4) were selected for the multivariable Cox analysis. The cut-off of ≤ 0.15 p-value was used in order to include the presence of resectable liver metastases as that is a well-known prognostic factor in mCRC. In the second step multivariable Cox regression analysis was performed including those variables identified in the univariate analysis. Importantly, the variable treatment (FOLFIRI vs FOLFOX) was not included for the development of the prediction score because it was not a characteristic intrinsic to the patients.

--	--

12-MONTHS PFS RISK MODEL DEFINITION

Clinical variables and biomarkers were used to build a score to predict 12-months PFS, by using a multivariable Cox regression model built with those clinical variables with a $p \leq 0.15$ in the multivariable analysis (performance status, chemotherapy regimen, sidedness, resectable only liver metastases). Once the first risk score was built adding up the coefficients of the multivariable model ($PS > 0 = 0.6$, left sided = -0.5, resectable liver only metastases = -0.4 and folfiri+cetuximab therapy = Not evaluable), ROC curves were computed for PFS at 12 months using a logistic regression model. All 4 scores (A. Clinical variables including PS, sidedness and resectable only liver metastases, B. Clinical variables + BRAF mutation; C. Clinical variables + PI3K mutation or PTEN ≤ 3 ; D. Clinical variables + DP) had comparable low areas under the curve, ranging between 0.5 and 0.7, overall: The AUC of the score containing the clinical variables was 0.67 (95% CI) (0.60-0.75).

The AUC of the score with clinical variables and BRAF mutational status was 0.68 (0.61-0.75, p-value = 0.37). The AUC of the score with clinical variables and PI3KCA mutation/PTEN status was 0.69 (0.61-0.76, p-value = 0.32). The AUC of the score with clinical variables and DP phenotype was 0.66 (0.58-0.73, p-value = 0.09).

SAFETY RESULTS

CONCLUSIONS

DATE OF THE REPORT:

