6.5.1.5. Analysis of main study variables

The primary efficacy analysis of this trial was performed based on all subjects who provided their informed consents, were included in the trial, and did not present significant protocol deviations throughout the study period. .

Continuous and ordinal variables between independent groups were compared using the Wilcoxon rank-sum test and proportions were compared with Fisher's exact test. Clinical endpoints were ORR, DoR, PFS, and OS. Tumour assessments by CT scans were performed every 3 months until PD. Patients without a second CT scan evaluation were not assessable for ORR.

PFS was defined as the time of the signature of the ICF date until PD or death from any cause. Patients who did not experience PD or death were censored on the date of last examination. For more information regarding censoring see in Section 7.5.1.1. OS was defined as the time from the signature of the ICF date to death from any cause. Patients lost to follow-up or still in the study at database closure have been censored at the date last known to be alive.

Survival analyses including PFS and OS were performed using Kaplan–Meier methods. Cox proportional hazards regression with the Efron method for ties was used to identify prognostic factors for PFS and OS.

Multivariable analysis was performed using subject-matter knowledge and deciding a *priori* the variables to adjust by age (>65 years), sex, tumour site (right vs left), surgery of primary tumour, liver only metastases (<3 nodules and <5 cm vs >3 nodules or >5 cm), ECOG PS, LDH (>450 U/L) and CEA, BRAF mutational status, and type of therapy. This analysis was later adjusted by variables with p-values <0.10 in the

univariate analysis via the automated stepwise selection of variables (p-value for variable entry into the model was 0.2 and p-value to keep the variable in the model was 0.1).. All p-values were two sided.

The proposed sample size ensures establishing a consistent multivariable analysis. Clinical variables and biomarkers were used to build scores intended to predict 12- months PFS as following:

1. A multivariable Cox model was built with those clinical variables that in the univariate analysis had a p-value ≤ 0.15 (PS, chemo regimen, sidedness, resectable liver metastases).

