2. A score was established for each patient by adding up the regression coefficients of the multivariable Cox model present in these patients. If for example PS>0 was a negative predictor for PFS (i.e. regression coefficient is negative; e.g. -0.5) and left side tumour was a positive prognostic factor (regression coefficient was positive, e.g. 0.6) then for a patient with PS>0 and left sided tumour the two scores were added (-0.5 + 0.6=0.1). If a patients has PS=0 then the score to be added is 0, as it is the case for right sided tumour in the example.
3. Using a logistic regression model for the outcome 12-months PFS, a ROC curve was computed to choose the score cut point that classifies most patients correctly 4. Patients were dichotomized according to that cut point.
5. Steps 2 to 4 were repeated, adding each of the three biomarkers.
6. Definition of the discriminating power of the 4 scores for prognosis of or 12-months PFS according to these results were compared via ROC curves.
7. Determination of the most suitable score for 12-months PFS according to these results.

The four scores included in the first multivariate model using clinical factors where PS>0, chemotherapy with FOLFIRI and cetuximab, left sided and resectable liver metastases were considered (Score 1). The additional scores considered the four clinical factors above plus the status of each biomarkers (Score 2: BRAF mutation; Score 3: PI3K mutant or PTEN ≤ 3) and Score 4: Double-positive Phenotype (DP).

All analyses were performed using SAS V9.3 (SAS Institute, Cary, NC, USA) statistical software.

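### SAP 6.5.1.5 builds, cuts and chooses the PFS score in the same patients without internal validation, so the reported AUCs are modestly optimistic; the SAP also defines the score in two incompatible ways.

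*SAP*

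**What the plan says.** SAP 6.5.1.5 sets out seven steps.

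- **Screening and weights.** Clinical variables are filtered on their association with PFS: "A multivariable Cox model was built with those clinical variables that in the univariate analysis had a p-value" of 0.15 or less. The fitted coefficients become the weights: "A score was established for each patient by adding up the regression coefficients of the multivariable Cox model present in these patients".
- **Cut point.** With a logistic model for 12-month PFS, "a ROC curve was computed to choose the score cut point that classifies most patients correctly", and patients are split there.
- **Choice among scores.** The work is repeated with BRAF, PI3K/PTEN and DP added in turn. The last step is "Determination of the most suitable score for 12-months PFS according to these results".

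The SAP synopsis says that every clinical variable collected was screened. On the limit it states: "The cut-off of ≤ 0.15 p-value was used in order to include the presence of resectable liver metastases", giving as its reason that this is an established prognostic factor. It reports AUCs of 0.67 (0.60–0.75) for the clinical score, and 0.68, 0.69 and 0.66 with BRAF, PI3K/PTEN and DP added (p = 0.37, 0.32 and 0.09).

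The two descriptions of the score differ. The synopsis says that "the variable treatment (FOLFIRI vs FOLFOX) was not included for the development of the prediction score" and lists the FOLFIRI weight as not evaluable. In 6.5.1.5 the clinical factors of the first score include "chemotherapy with FOLFIRI and cetuximab, left sided and resectable liver metastases were considered (Score 1". The synopsis first applies the 0.15 limit to the univariate analysis. Under its risk-model heading it applies the limit to variables "in the multivariable analysis (performance status, chemotherapy regimen, sidedness, resectable only liver metastases". Section 6.5.1.5 applies it to the univariate analysis only.

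**The concern.** Every step that shapes the score looks at the outcome on which the score is then assessed. An AUC obtained this way describes fit in these patients and overstates discrimination in new ones. Neither document provides a correction, although the protocol calls its aim validation. A reader could take 0.67 as performance to expect elsewhere.

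The contradiction matters separately. Until it is settled whether regimen is in the score and which filter was used, the score cannot be reproduced and no resampling of the procedure can be specified.

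A further matter is conditional. Protocol 10.2.5, the SAP synopsis and SAP 6.5.2 size the trial for a log-rank comparison of two groups at two-sided 5%. If that test were run on groups cut from this score in the same patients, its p-value would not have its nominal meaning.

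**Working it through.** **Inputs from the documents.** Efficacy set 181 (SAP synopsis). Reported weights 0.6 for PS>0, −0.5 for left-sided tumour and −0.4 for resectable liver-only metastases (SAP synopsis). Biomarker-positive counts 20/181, 98/167 and 23/181 (SAP Table 6). Filter p ≤ 0.15. The number of variables screened is not fixed in the text available, so a range was used:

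- 4: clinical variables in protocol 10.4
- 9: a priori list in SAP 6.5.1.5 without BRAF
- 12: lines of SAP 6.5.1.4
- 19: characteristics in Table 6

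**Assumptions.** Exponential PFS, binary independent candidates, no censoring before 12 months, and biomarkers with no effect. Setting A has median PFS 10 months, that is 12-month PFS of 0.5^(12/10) = 0.44. Setting B has 12-month PFS 0.40 and covariate prevalence 0.4. AUCs are for the undichotomised score.

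**1. The plan's own figure.** With the reported weights as truth and the three variables fixed in advance, setting B gives a mean apparent AUC of 0.672, against the reported 0.67. The model is a fair stand-in.

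**2. AUC optimism of the clinical score** (apparent AUC minus AUC in new patients):

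| Candidates | Setting A | Setting B |
|---|---|---|
| 3, fixed in advance | 0.660 − 0.650 = 0.010 | 0.672 − 0.661 = 0.011 |
| 4 screened | 0.666 − 0.643 = 0.023 | not run |
| 12 screened | 0.676 − 0.644 = 0.032 | 0.684 − 0.647 = 0.037 |
| 19 screened | 0.690 − 0.646 = 0.044 | 0.694 − 0.641 = 0.053 |

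Applied to the reported value: 0.67 − 0.01 = 0.66 down to 0.67 − 0.05 = 0.62. For the best of four scores in setting A, optimism is 0.679 − 0.641 = 0.038 (4), 0.685 − 0.642 = 0.043 (12) and 0.698 − 0.644 = 0.054 (19).

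**3. Does a bootstrap repair it?** Setting A, 150 trials with 50 resamples each, repeating filter, weights and choice of score. Corrected against true AUC for the best of four: 0.650 and 0.641 (4), 0.635 and 0.642 (12), 0.635 and 0.644 (19). The error is below 0.01. For the clinical score alone it is at most 0.011.

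**4. The biomarker increments.** Reported: 0.68 − 0.67 = 0.01, 0.69 − 0.67 = 0.02, 0.66 − 0.67 = −0.01. The best in-sample gain from three useless biomarkers averaged 0.016 to 0.021 when nothing predicted PFS, and 0.008 to 0.010 with the reported clinical weights. Reported gains of this size are no evidence for the biomarkers, and the SAP's p-values claim none.

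**5. Conditional: log-rank at 5% on score-defined groups under a global null** (setting A, 2,000 trials per scenario; each range runs from the clinical score to the best of four):

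| Candidates | As in 6.5.1.5 | As in the synopsis |
|---|---|---|
| 4 | 21–30% | 16–25% |
| 9 | 44–51% | 37–44% |
| 12 | 53–60% | 46–53% |
| 19 | 76–80% | 67–72% |

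The synopsis column applies the second 0.15 filter and leaves regimen out. The pre-named biomarker categories gave 5–6%. Most of the excess comes from screening and fitting. With fitted weights, a median cut already gives 20% (4) and 52% (12), and choosing the cut adds 1 to 2 points. A permutation test that repeats every step gave 5.8% (4) and 5.2% (12).

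**The case against.** The strongest reply is that the SAP's primary analysis (6.5.1.1) compares the clinical AUC with the clinical-plus-biomarker AUC for three categories named in advance. The synopsis already calls the AUCs low, the optimism is a few hundredths, and no conclusion changes. All of this stands. Screening also flatters the clinical comparator, so the bias in the increment can go either way.

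Three stronger readings are tempting, and the documents do not support them.

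- **That the trial's type I error is 16 to 80%.** Steps 1 to 7 contain no log-rank test, and no visible result table has a p-value between score groups. Protocol 10.2.5 uses the log-rank for the sample-size calculation. Protocol 10.2.1, the evaluation criteria in the SAP synopsis and SAP 6.5.1.1 do not mention it. SAP 6.5.2 speaks of established categories of clinical variables, and other passages point to single-biomarker groups. A global null is also implausible, because protocol 4.5 and SAP 4.2 describe performance status and LDH as prognostic and protocol 10.4 pre-names functional status and limited resectable disease.
- **That the 0.15 limit is stated to have been set after seeing the data.** The sentence strongly suggests it, but it also gives a subject-matter reason. It remains an inference.
- **That the screened variables were never listed.** The synopsis refers to Appendix 15.2, item 4, which is not among the documents reviewed and may contain the list.

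The reply does not answer the uncorrected absolute AUCs or the two definitions of the score.

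**Conclusion.** The point holds in a limited form. The apparent AUCs are optimistic by about 0.01 if the three weighted variables were effectively fixed in advance, and by 0.02 to 0.05 if 4 to 19 candidates were screened. The clinical score's 0.67 would then be about 0.62 to 0.66, within its own interval. The size rests on the simulation assumptions above and on a candidate count that cannot be confirmed here. The direction does not depend on them. The contradiction over regimen and filter is plain from the text.

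The log-rank matter is secondary and applies only if the two groups are cut from the score in the same patients. A significant split would then not validate the biomarkers, since clinical variables alone can produce it. Log-rank tests on the pre-named biomarker categories are unaffected.

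**What to change.** 1. **Reconcile the SAP synopsis with 6.5.1.5.** State whether regimen enters the score and whether the 0.15 filter is univariate or multivariable. List every variable screened, or point to Appendix 15.2, item 4, if the list is there.
2. **Add after step 7:** the whole reconciled procedure (filter, weights, choice of score, and cut point if the dichotomised score is assessed) is repeated in bootstrap samples, and optimism-corrected AUCs are reported beside the apparent ones. State whether the AUCs use the continuous or the dichotomised score, which steps 4 to 6 leave open. Add that the choice of the 0.15 limit appears data-informed and is not captured by the resampling.
3. **State which two groups the log-rank test in the synopsis and 6.5.2 compares.** Label any p-value between score-defined groups descriptive, or replace it with a permutation p-value that repeats every step. That test addresses only the global null, so say that it does not validate the biomarkers.

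The cost is SAP wording and some programming on existing data. The downside is slightly less favourable AUCs, with some optimism possibly left from the choice of limit. In one model of that choice (the lowest of 0.05, 0.10, 0.15 and 0.20 that admits resectable liver metastases), the remaining error was about 0.01 or less.

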- h. If thoracic CT scan at selection did not show any chest abnormality, chest X-ray imaging were performed in subsequent evaluations. A CT scan was performed to confirm any abnormality identified upon chest X-ray imaging performed after selection, and all subsequent evaluations were thoracic CT imaging.
- i. Response evaluation was conducted according to the revised RECIST 1.1 criteria, every 12±1 weeks until PD. Subject follow-up was performed regardless of discontinuation or a delay in treatment.
- j. ECOG PS evaluation (on day 1 of each treatment cycle).
- k. Tumour evaluation and serum CEA test was performed every 12 weeks and at the follow-up visit only in subjects who have withdrawn from the trial for reasons different from PD, and in those who have not had a serum CEA test in the previous 12 weeks.
- l. Paraffin embedded tumour block was sent to the central laboratory (Fundación Jiménez Díaz) at selection. The centralised evaluation laboratory perform a tumour block quality assessment. It was compulsory that KRAS and NRAS mutational status (wtKRAS and NRAS) was confirmed by a validated laboratory before the inclusion of any subject.
- m. Follow-up of all subjects who permanently discontinued the treatment before disease progression (e.g. due to unacceptable toxicities) was conducted to evaluate PFS (i.e., tumour imaging) every 12± 1 week until PD or until the end of study (unless the reason for study discontinuation was total consent withdrawal). After PD, all subjects underwent a follow-up assessment of disease status, subsequent cancer therapy, and survival assessment every 12 ± 1 weeks until the end of study (maximum of 24 months).
- n. Blood samples for biomarker analysis were withdrawn before the study treatment initiation and every 12 weeks ± 1 weeks until PD.

Table 3: SDV schedule

Form	Variables
Eligibility	Pathology report, staging, prior treatment.
Demographics	Date of birth, ECOG PS, ICF (signature, date, and completion)
Primary tumour	Diagnosis date, location, staging and surgery
Adjuvant or neoadjuvant treatment	Yes/No
KRAS/NRAS	Central reviewing
Baseline biochemistry and SAE biochemistry	LDH, creatinine, bilirubin, and CEA
Baseline haematology and SAE haematology	Haemoglobin, platelets, and leukocytes

Metastasis	Nº affected organs and hepatic M1 (number and size)
CT scans or MRI	All variables (date, lesions measure, location, new lesions) and RECIST criteria
AEs	Grade and need of SAE communication

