6.5 STATISTICAL METHODS PLANNED IN THE PROTOCOL & DETERMINATION OF SAMPLE SIZE

6.5.1 STATISTICAL AND ANALYTICAL PLANS

6.5.1.1. Primary endpoint

To quantify if the biomarkers BRAF, IGF-1RP/MMP-7 (DP), DP and PIK3CA-PTEN improve the prediction of 12-months progression-free survival (PFS) over the use of just clinical variables in the study population we compared the area under the curve (AUC) of a ROC curve using scores composed by clinical variables with the AUC of scores with the clinical variables plus each of the biomarkers.

PFS was defined as the time from the signature of the ICF date to the radiological progression date or death (whatever occurs first). Subjects who had not shown PD and had not died at database closing were censored on the last date of radiological assessment. Subjects who had concluded study treatment before 48 weeks, due to any cause, underwent follow-up every 12 weeks as described in the protocol. Subjects who had undergone metastatic surgery were not censored on the surgery date but were followed up every 12 weeks until progression was documented. Subjects who received other treatment schemas maintaining the same strategy (chemotherapy + monoclonal antibody) without documented PD, were not censored at the time of the change of treatment. Progression to first line for these patients was considered when applicable according RECIST, independently of treatment received. If by any cause, the baseline CT scan was the only imaging evaluation performed (e.g., subject refusal to stay in the study or lost to follow-up), the case was censored on the inclusion date +1 day.

Two groups with a higher and lower likelihood for tumor progression until 12 months were determined based on the designated classification of clinical variables and following proposed biomarker categories :

1. wt-BRAF vs mutant BRAF

2. wtPI3K and PTEN >3 vs mutant PI3K or PTEN ≤3
3. Non-DP vs DP

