6.5.1.4. Covariate analysis

The following baseline characteristics were studied by biomarkers in order to properly categorise the sample:

- Gender
- Age
- Primary Tumour location and sidedness (ascending colon, transverse colon, descending colon, sigma and rectum)
- Stage of the disease
- Surgery of the primary tumor
- ECOG Performance Status
- Number of metastatic organs
- Specific locations of metastasis including number, size and location node, lung, peritoneal and liver (considering also those patients with only resectable liver metastases for comparison)
- Mean values of haematological tests including leucocytes, haemoglobin, platelets,.
- Baseline LDH levels >450

- Mean ALP and Mean CEA
- Chemotherapy (FOLFOX+Cetuximab /FOLFIRI+Cetuximab)

These groups have been used for univariate and multivariable analysis in order to evaluate efficacy variables such as ORR and PFS. Disease response was clinically assessed by the investigator based on the radiological imaging data collected throughout the study. Any finding considered as non-assessable by the investigator was excluded from the analysis (it was considered as non-existent).

For continuous variables, mean, standard error (for efficacy variables), standard deviation (for other measurements), median, 25th percentile, 75th percentile, minimum and maximum, were evaluated. Categorical variables were presented using frequencies and percentages.

The 95% two-sided confidence intervals (95%CIs) of Kaplan–Meier quartiles for time to event variables were calculated according to Brookmeyer and Crowley methods (Brookmeyer, 1982). The 95% two-sided CIs for the Kaplan–Meier estimates at various time points were calculated according to the methods described by Collett (Collett, 1992).

Safety data were analysed throughout the entire study and presented by descriptive analysis.

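### The primary 12-month ROC comparison and score cut point make no adjustment for PFS censored before month 12, and the SAP does not say how such patients are coded

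*SAP*

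**What the plan says.** SAP 6.5.1.1 (Primary endpoint) describes the primary analysis: "we compared the area under the curve (AUC) of a ROC curve using scores composed by clinical variables", set against scores that add each biomarker. SAP 6.5.1.5 gives the method in step 3: "Using a logistic regression model for the outcome 12-months PFS, a ROC curve was computed to choose the score cut point". Step 4 splits patients at that cut point, step 5 repeats the procedure with each biomarker, and step 6 compares the ROC curves. The SAP Synopsis agrees: "ROC curves were computed for PFS at 12 months using a logistic regression model".

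SAP 6.5.1.1 also defines PFS as a censored time:
- "Subjects who had not shown PD and had not died at database closing were censored on the last date of radiological assessment".
- If only the baseline CT exists, "the case was censored on the inclusion date +1 day".
- Patients who change treatment within the same strategy (chemotherapy plus antibody), without documented progression, "were not censored at the time of the change of treatment".

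Scans follow this rule in the SAP section 6 schedule: "Response evaluation was conducted according to the revised RECIST 1.1 criteria, every 12±1 weeks until PD". Scans judged non-evaluable count as not done (SAP 6.5.1.4).

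Elsewhere the SAP uses methods that handle censoring: Kaplan-Meier estimates with intervals at chosen time points (6.5.1.4) and Cox models for the score coefficients (6.5.1.5). Neither document says how a patient censored before month 12 enters the logistic and ROC step, and neither mentions weighting or a time-dependent ROC.

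**The concern.** With the score as the only predictor, the logistic model does not change the ranking of patients. The AUC therefore depends on just two things: the score, and each patient's status at 12 months. That status is unknown for anyone censored earlier. Such a patient can be coded progression-free, coded as a failure, or dropped. The choice is made in the step that produces the primary comparison and the cut point defining the two cohorts, yet the SAP leaves it open.

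The reported contrasts are small. If the coding choice can move an AUC difference by a similar amount, a reader cannot tell whether a biomarker's apparent gain or loss belongs to the biomarker or to the handling of early drop-outs.

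**Working it through.** **1. The plan's own figures.** The SAP gives no count of patients censored before month 12, and its disposition table (Table 4) is an empty shell, so there is no stated figure to reproduce. The Synopsis gives AUCs of 0.67 for the clinical score (95% CI 0.60-0.75), 0.68 with BRAF, 0.69 with PI3K/PTEN and 0.66 with DP. The differences are +0.01, +0.02 and -0.01.

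**2. Who can be censored before month 12.** SAP 6.5.2 gives 47 months of recruitment within 70 months in total. Minimum potential follow-up is 70 - 47 = 23 months, so database closure alone should censor nobody before month 12. Loss, withdrawal, missed or non-evaluable scans and baseline-only cases remain. Timing also matters. Week 48 is 48 × 7 / 30.44 = 11.04 months. PFS starts at consent, and selection may precede cycle 1 by up to 28 days. If scans are timed from treatment, the week-48 scan falls between 11.04 and (336 + 28) / 30.44 = 11.96 months after consent, before the ±1-week window. On nominal timing, a patient clear at that scan with no later one has no 12-month status.

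**3. Simulation inputs.**
- From the SAP: coefficients 0.6 (PS>0), -0.5 (left-sided) and -0.4 (resectable liver-only) from the Synopsis; marker prevalence 11%, in line with BRAF in Table 6 (20/181); hazard ratio 1.79 from 6.5.2, applied here to the marker.
- Assumed: exponential PFS, PS>0 50%, left-sided 70%, resectable 10%, and all censoring shares and patterns.
- True values: 12-month PFS 39.6%, clinical AUC 0.656, marker gain 0.0155.

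**4. Results by coding of early-censored patients.** Ten percent is about 18 of 181.

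| Early censoring | Quantity | Coded progression-free | Dropped | Coded failure |
|---|---|---|---|---|
| Independent, 10% | AUC (true 0.656) | 0.645 | 0.657 | 0.642 |
| Independent, 9% | Gain (true 0.0155) | 0.0146 | 0.0156 | 0.0141 |
| 4 times as frequent in PS>0, 10% | AUC (true 0.656) | 0.621 | 0.670 | 0.677 |
| 3 times as frequent in marker-positives, 11% | Gain (true 0.0155) | 0.006 | 0.018 | 0.022 |

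For independent censoring the AUC shifts are -0.011, +0.001 and -0.014, and the gain moves by at most 0.0155 - 0.0141 = 0.0014. For PS-dependent censoring the largest AUC shift is 0.656 - 0.621 = 0.035 (up to 0.037 in repeat runs), but the gain stays within 0.0125-0.0158. For marker-dependent censoring the gain shifts by -0.0095, +0.0025 and +0.0065.

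**5. Sensitivity to the share censored.** With PS-dependent censoring the three AUCs are 0.638, 0.663 and 0.667 at 5%, and 0.649, 0.659 and 0.660 at 2%. With independent censoring at 20% the gain runs from 0.0131 to 0.0160.

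A second set of assumptions used PS>0 55%, resectable 15%, 12-month PFS 38% and true AUC 0.663. At 10% censoring tied to good prognosis, the worst coding gave 0.611, a shift of 0.052. At 2% the largest shift was 0.011.

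**6. Censoring-adjusted estimate.** Let G(t|Z) be the probability of being uncensored at t given covariates Z. Weight each observed event at T ≤ 12 by 1/G(T|Z) and each patient known progression-free at 12 by 1/G(12|Z), then compute the ordinary AUC. This returned the true values within 0.001 in every scenario. The weights used the mechanism that generated the censoring, so this shows the method is correct when G is right, and no more.

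**The case against.** The strongest reply is that early censoring may be too rare to matter. Follow-up was long, surgery does not censor, a same-strategy change of treatment does not censor, and patients who stop early are still scanned every 12 weeks. Under independent censoring, simply dropping patients does almost no harm to the AUC, and the AUC difference is more stable than the AUC level. The shifts are also small beside a confidence interval of 0.60-0.75. All of this stands, and it limits the severity. It does not settle how these patients were coded, and it gives no protection if censoring depends on the marker.

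A reader might infer that every AUC, cut point and 12-month rate is biased, or that the error must be at least as large as the reported AUC differences. The documents do not support either. The actual share and pattern of early censoring are unknown, the 12-month rates come from Kaplan-Meier, and the gain moved by about 0.01 only when censoring depended on the marker and those patients were coded progression-free.

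Two other inferences should be avoided. Table 7 lists 24 + 2 + 2 + 49 = 77 treatment stops by investigator decision, but those patients stay in follow-up and are not a count of censored patients. The protocol's 28-month schedule would have left 28 - 24 = 4 months' minimum follow-up and about 19-22% administratively censored before month 12 under the assumed effect sizes. The trial did not run on that schedule.

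**Conclusion.** The point holds at moderate severity. The primary AUC comparison and the cohort-defining cut point rest on a yes/no outcome taken from a censored time, with no adjustment and no stated rule for patients censored before month 12. The Cox coefficients and Kaplan-Meier rates are not affected.

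The size depends on coding and on who is censored. At about 10% early censoring:
- the AUC level can move by about 0.01-0.015 through miscoding alone, and by about 0.036 if censoring depends on performance status;
- the gain barely moves under independent censoring, but a true 0.0155 can become 0.006-0.022 if censoring depends on the marker, against reported differences of -0.01 to +0.02.

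At 2% the shifts in AUC level are at most about 0.01. These figures rest on the assumed prevalences, exponential PFS and assumed censoring patterns. The shift in the cut point was not quantified.

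**What to change.** In SAP 6.5.1.5, steps 3-6, and in the Synopsis:
- Compute the 12-month ROC curves, AUCs and cut point with a cumulative/dynamic time-dependent ROC using inverse-probability-of-censoring weights, with the censoring model depending on measured covariates such as performance status, regimen and marker status.
- Keep the logistic ROC as a sensitivity analysis, and state how patients censored before month 12 are coded in it.
- Report the number censored before month 12 by score group and by marker group, with reasons. If it is close to zero, the two analyses will agree and the matter is closed.
- State whether a treatment change outside the same strategy, without progression, censors PFS. Protocol 10.2.1 censors at second-line treatment, and SAP 6.5.1.1 addresses only same-strategy changes.

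The cost is SAP wording, a little code and slightly wider intervals. No new data are needed. The weights assume that censoring depends only on measured covariates, and the report should say so.
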